X 5. Research involving materials (data, documents, records, or specimens) that have been collected, or will be collected solely for nonresearch purposes (such as medical treatment or diagnosis). (NOTE: Some research in this category may be exempt from the HHS regulations for the protection of human subjects. 45CFR 46.101(b)(4). This listing refers only to research that is not exempt.)

Retrospective chart review of data that has already been obtained (2011-2014). We will evaluate SLU hospital's medical health record system for this data.

- 6. Collection of data from voice, video, digital, or image recordings made for research purposes.
- 7. Research on individual or group characteristics or behavior (including, but not limited to, research on perception, cognition, motivation, identity, language, communication, cultural beliefs or practices, and social behavior) or research employing survey, interview, oral history, focus group, program evaluation, human factors evaluation, or quality assurance methodologies. (NOTE: Some research in this category may be exempt from the HHS regulations for the protection of human subjects. 45 CFR 46.101(b)(2) and (b)(3). This listing refers only to research that is not exempt.)
- 8. [FOR IRB use only]. Continuing review of research previously approved by a convened IRB only when condition (a), (b), or (c) is met.
 - a) Previously approved research where
 - (i) The research is permanently closed to the enrollment of new subjects;
 - (ii) All subjects have completed all research-related interventions; and
 - (iii) The research remains active only for the long term follow-up of subjects.
 - b) Previously approved research where no subjects have been enrolled and no additional risks have been identified.
 - c) Previously approved research where the remaining research activities are limited to data analysis.
- 9. [FOR IRB use only]. Continuing review or research not conducted under an investigational new drug application or investigational drug exemption where expedited categories two (2) through eight (8) do not apply but the IRB has determined and documented at a convened meeting that the research involves no greater than minimal risk and no additional risks have been identified.

Protocol # 29062 [name]

Protocol Title:	Percutaneous Endoscopic Gastrostomy (PEG) tube placed less than or greater than 7 days post stroke: Mortality, Predictors of Mortality, Complications, and Outcomes.
	-

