A study published in Annals of Gastroenterology identified markers that predict early mortality in post PEG patients (female, low albumin, positive urine culture).8 This study also evaluated whether markers for early mortality after PEG insertion could be used to predict length of hospital stay post-PEG. They identified mechanical ventilation, low albumin levels and present of 2 or more co-morbidities as predictors of late discharge.8 This study also raises the issues of providing a waiting period to preclude unnecessary PEGs in patients likely to die in the immediate post- PEG placement period.8

Patients who suffer from a stroke require either intensive inpatient rehab post stroke or a skilled nursing facility. In order to be discharged from the hospital to one of these facilities, patients must either be able to resume oral nutrition or a PEG tube must be in place. Facilities do not accept patients with nasoenteral tubes, as these tubes have a high risk of displacement and treatment failure.2,3 Thus, the demand to initiate early PEG tube placement and feedings post stroke has risen.

There are no studies comparing the outcomes of early PEG placement (<14 days post stroke) versus late PEG placement (> 14 days post stroke). It is important to evaluate the procedural and post-procedural complications of PEG tubes, mortality, predictors of mortality and overall patient outcomes. Addressing these questions will provide better evidence for timing of PEG tube placement in post stroke patients, which will aid the ultimate goal, better patient care.

Bibliography:

- 1.ASGE Guideline. Role of endoscopy in enteral feeding. ASGE 2011; 74: 7-12.
- 5. World Health Organization ICD. http://www.who.int/classifications/icd/en/

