- 4.To evaluate predictors of mortality. Factors that will be evaluated include: sex, age, comorbidities (dementia, diabetes, CAD), laboratory values including leukocytosis prior to procedure, blood/urine culture, albumin).

Please save frequently

c) Describe the study design (e.g., single/double blind, parallel, crossover, control, experimental, observational, etc.). If the study is investigator-initiated, a timeline for individual subject recruitment, follow-up, and analysis for the study is required. Also, indicate if the subjects will be randomized.

This study is a retrospective chart review. We are unsure of the number of patients, but will estimate approximately 150 patients total, with 75 patients with PEG placed before 7 days since acute dysphagic stroke and 75 patients with PEG placed after 7 days for acute dysplagic stroke. Should our search criteria yield fewer or more patients than expected, then we will simply report the total number of patients that fit our inclusion and exclusion criteria. Patients will be enrolled from St. Louis University Hospital (SLU) along with other SSM hospitals. We will use data from our medical record system, Epic, and also the gastroenterology procedure

Protocol Title:

Percutaneous Endoscopic Gastrostomy (PEG) tube placed less than or greater than 7 days post stroke: Mortality, Predictors of Mortality, Complications, and Outcomes.

.-----

documentation program ProVation. We will include patients from 2011-2014 who underwent PEG tube placement post acute dysphagic stroke. Patients will be included in the study by evaluating International Classification of Diseases (ICD) codes associated with each patient's admission as well as ProVation biling diagnosis of PEG tube placement. ICD is a healthcare classification system, providing a system of diagnostic codes for classifying diseases.

PEG tubes were placed endoscopically using the standard "pull through" technique described by Ponsky and Gauderer.7 We will not be including PEG tubes placed surgically or radiologically. All patients were admitted to the hospital at the time of the PEG insertion and were post acute dysphagic stroke. A dose of antibiotics, most times, Ancef 1 gm IV 30 minutes prior to the procedure was given. However, other antibiotics with similar spectrum of coverage may have been used. The PEG site was examined for infection and bleeding 24 hours after insertion and tube feeds were subsequently recommended at that time.

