Percutaneous Endoscopic Gastrostomy (PEG) tube placed less than or greater than 7 days post stroke: Mortality, Predictors of Mortality, Complications, and Outcomes.

classification system, providing a system of diagnostic codes for classifying diseases.

PEG tubes were placed endoscopically using the standard "pull through" technique described by Ponsky and Gauderer.7 We will not be including PEG tubes placed surgically or radiologically. All patients were admitted to the hospital at the time of the PEG insertion and were post acute dysphagic stroke. A dose of antibiotics, most times, Ancef 1 gm IV 30 minutes prior to the procedure was given. However, other antibiotics with similar spectrum of coverage may have been used. The PEG site was examined for infection and bleeding 24 hours after insertion and tube feeds were subsequently recommended at that time.

c) If the proposed study is a clinical trial where a drug, vaccine, device or other treatment is compared to a placebo group or comparison treatment group, what are the guidelines or endpoints by which early decisions regarding efficacy or lack of efficacy can be made? For example, it may be reasonable to stop enrollment on a study when efficacy has already been clearly demonstrated, to avoid unnecessary enrollments of additional subjects. Alternatively, it may be reasonable to stop enrollment when it is clear that efficacy will never be demonstrated, given the statistical power of the study as designed. Describe the guidelines that are in place to assist in making these determinations, if relevant to the proposed study.

N/A

d) Describe how data analysis will be performed (statistical tests, methods of evaluating data) and indicate the smallest group/unit for which separate reporting will occur. For studies involving a questionnaire, if data and reliability information are available, please describe or provide references. For full board, unfunded studies describe sample size determination and power analysis. If none, please justify.

Sample size calculation for this particular study is not feasible. This is a single center study and we are limited to the number of patients who have received PEG tubes at this institution and we cannot create a large sample size. Thus, no sample size calculation is needed. All patient's who fit the inclusion criteria will be included in this study.

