Patient characteristics will be described using means and medians for continuous variables and frequencies (percents) for categorical level variables. Comparisons between PEG groups will be made using t-tests (continuous data) or chi-squared (categorical data). To address the main study objective, survival analysis will be conducted, using a log-rank test to compare overall survival between groups. Secondary objectives will be analyzed using chi-squared tests. Additional statistical analyses will be used when appropriate. Statistically significant differences are defined as alpha<0.05. All analyses will be performed using SPSS version 22.0.

Please save frequently

- e) State if deception (including incomplete disclosure of study purpose/procedures) will be used. If so, describe the nature of the deception and provide a rationale for its use. Also, describe debriefing procedures or justify a waiver of the requirement to debrief. NOTE: for studies using deception, an alteration of consent must be justified in the Informed Consent section of the protocol (#13) and the debriefing script/statement must be uploaded in the Attachments section (#16). See IRB Deception Guidelines.
- f) Is there an accepted standard of care and/or standard practice at SLU for the condition/disease/situation being studied? This information will assist in comparing the risk/benefit ratio of study procedures relevant to usual care that would be

Protocol # 29062 [name]

Protocol Title:

Percutaneous Endoscopic Gastrostomy (PEG) tube placed less than or greater than 7 days post stroke: Mortality, Predictors of Mortality, Complications, and Outcomes.

...........

the risk/benefit ratio of study procedures relevant to usual care that would be received outside of the research context. *?HELP?*

If yes, please describe the standard of care and standard practice at SLU for the condition/disease/situation being studied.

g) Does this study involve any diagnostic imaging, labwork or genetic testing that could N result in clinical discovery (diagnoses, genetic mutations, etc.)? Note that this could include discovery that is expected (related to the research) or incidental (not related to research aims, but possible, like a mass/shadow found in imaging despite not looking for it).

If yes, please describe and include whether there are plans to share findings with study participants.

h) Is this study subject to the NIH Genomic Data Sharing Policy?

Ν

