5. SSMSL

All research involving SSMSL locations (including Cardinal Glennon), including inpatient or outpatient services and medical record access, requires approval from the SSM STL or SSM Cardinal Glennon Research Business Review (RBR) prior to study initiation. This process is designed to facilitate compliance with state and federal regulations as they pertain to research in hospitals and clinical research billing. While researchers can begin to complete the SSM RBR form at any time, the form should not be submitted until the IRB and the CTO have approved the study. Please contact the SSMSL Office at [name] or [name]. [contact] for more information.

Not Applicable

- X Yes, study requires RBR review
- Does this project require registration on ClinicalTrials.gov, and/or is this project subject to the NIH GCP Training Requirement? (Select "Yes" if either apply)

Registration may be required if any of the following apply: 1) The project meets the FDAAA definition of an "Applicable Clinical Trial", which requires registration on ClinicalTrials.gov. 2) As of January 1, 2017, a new NIH policy mandated biomedical and behavioral "Clinical Trials" to be registered on ClinicalTrials.gov. In addition, NIH policies require personnel on NIH "Clinical Trials" to take GCP training every three years. 3) Registering may be required for Journal Publication (ICMJE). Please review relevant definitions here. Contact the CTO at [contact] with questions about registering on ClinicalTrials.gov and refer to the training page of the IRB website for

Ν

Protocol # 29062 [name]

	CC		

Percutaneous Endoscopic Gastrostomy (PEG) tube placed less than or greater than 7 days post stroke: Mortality, Predictors of Mortality, Complications, and Outcomes.

information on NIH GCP Training requirements.

* * * Subject Population * * *

- 8. Subject Population In the space below, please detail the participants that you are requesting to recruit (include description of each group requested)
- a) Expected age range of subjects. (For example ≥ 18 yrs to 90 yrs).

≥18 years old

b) Number of evaluable subjects to be accrued at SLU or SLU site (this includes all sites under the direction of the SLU PI).

150 patients, 75 patients with PEG placed less than 7 days post stroke and 75 patients with PEG placed greater than or equal to 7 days post stroke

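### The protocol is contradictory on which hospitals contribute, and its mortality test ignores hospital and calendar period, so differences between them may be read as an effect of PEG timing

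*Protocol*

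**What the plan says.** **Hospitals.** Sections 2c and 3b both say "Patients will be enrolled from St. Louis University Hospital (SLU) along with other SSM hospitals". Section 7, item 5, on SSM locations, is ticked "Yes, study requires RBR review". Elsewhere the document points to one hospital:

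- Section 3d: "This is a single center study and we are limited to the number of patients who have received PEG tubes at this institution".
- Section 3a answers N to the question on multicenter or multi-site conduct.
- The expedited-review justification (category 5): "We will evaluate SLU hospital's medical health record system for this data".
- The HIPAA waiver in section 15 names only SLU Hospital's record systems.

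**Period.** Section 2c: "We will include patients from 2011-2014 who underwent PEG tube placement post acute dysphagic stroke".

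**Analysis.** Section 3d addresses the main objective by survival analysis, "using a log-rank test to compare overall survival between groups". Secondary objectives get chi-squared tests. No stratification, matching or covariate is stated for the timing comparison, although unspecified further analyses are left open. The mortality predictors in section 2b are patient characteristics and laboratory values and include neither hospital nor year. The data items in section 8g include the procedure date and time but not the treating hospital.

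**The concern.** Timing of PEG was not assigned by the study. Section 1a gives one reason for early placement that is not a patient characteristic: facilities that take stroke patients after discharge do not accept nasoenteral tubes. A pressure of that kind could act differently in different hospitals or years. If it did, and if mortality also differed between those hospitals or years because of stroke care, referral pattern or completeness of death records, the crude comparison would mix that difference with any effect of timing. The bias could go in either direction.

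Patient-level adjustment would deal with the part that arises from measured case mix. It would not deal with differences in care or record-keeping between hospitals or periods.

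**Working it through.** **1. Figures in the plan.** There is no power calculation to reproduce; section 3d says a sample size calculation is not feasible. The expected numbers agree: 75 + 75 = 150. The only 3-month mortality figure in the protocol is in section 1a, from a cited retrospective PEG series: 12/48 = 25%. It serves here only as an illustrative base rate.

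**2. Set-up (assumed).** There is no true timing effect. There are two equal strata of 75 patients, which may be two hospital groups or two periods. The share with early PEG is 0.5 + g in stratum A and 0.5 - g in stratum B. Three-month mortality is 0.25 - h in A and 0.25 + h in B. The protocol gives neither g nor h.

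**3. Spurious difference.**

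- Early mortality = (0.5 + g)(0.25 - h) + (0.5 - g)(0.25 + h) = 0.25 - 2gh
- Late mortality = (0.5 - g)(0.25 - h) + (0.5 + g)(0.25 + h) = 0.25 + 2gh
- Difference = 4gh, which is zero if either g or h is zero

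**4. False-positive rate at two-sided 0.05** (section 3d does not state sidedness). The normal approximation uses SE = sqrt(0.25 × 0.75 × 2/75) = 0.0707. It was checked by simulating exponential survival times censored at 90 days, with 2000 runs per setting.

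| g | h | Early | Late | Difference (points) | Normal approx. | Unstratified log-rank | Stratified log-rank |
|---|---|---|---|---|---|---|---|
| 0 | 0 | 25% | 25% | 0 | 0.050 | 0.052 | 0.0495 |
| 0.1 | 0.05 | 24% | 26% | 2 | 0.059 | 0.055 | 0.055 |
| 0.2 | 0.10 | 21% | 29% | 8 | 0.205 | 0.1955 | 0.043 |
| 0.3 | 0.10 | 19% | 31% | 12 | 0.396 | 0.4085 | 0.0525 |
| 0.3 | 0.15 | 16% | 34% | 18 | 0.721 | 0.7505 | 0.053 |

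The stratified test stays close to 0.05 throughout.

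**5. A worked example with other assumed rates.** Two hospitals of 75 patients have 3-month mortality of 20% and 35%. The first places 80% of its PEGs early, the second 20%.

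- Early: (60 × 0.20 + 15 × 0.35)/75 = 17.25/75 = 23.0%
- Late: (15 × 0.20 + 60 × 0.35)/75 = 24/75 = 32.0%

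The crude difference is 9 points and the difference within each hospital is zero. The formula agrees: 4 × 0.3 × 0.075 = 0.09.

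**6. Price of stratifying.** Information on the timing contrast is proportional to p(1 - p), where p is the early share. Pooled, this is 0.5 × 0.5 = 0.25. Within strata split 80/20 it is 0.8 × 0.2 = 0.16. The loss is 1 - 0.16/0.25 = 36%. With a 60/40 split it is 1 - 0.24/0.25 = 4%.

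**The case against.** **The study may be single-center.** If the single-center wording governs, the hospital half of the point falls away. The tick for SSM review does not settle it, since the phrase in section 2c counts SLU itself among the SSM hospitals. This stands, so the hospital part is conditional. The calendar-period part does not depend on it.

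**The evidence for a trend or for site differences is thin.** A reader might infer that demand for early PEG rose during 2011-2014. Section 1a says only "Thus, the demand to initiate early PEG tube placement and feedings post stroke has risen", as background, with no dates, size or hospital. A reader might also take "However, other antibiotics with similar spectrum of coverage may have been used" as evidence that practice differed between sites. That sentence is tied to no hospital or year, and the surrounding text describes one technique and one 24-hour site check. Neither passage shows imbalance; section 1a only makes it plausible.

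**Hospital may be collected anyway.** A reader might infer from section 8g that hospital will not be available. That list is plainly not exhaustive: it omits age, sex, albumin and cultures, which section 2b says will be evaluated. The approved data collection sheet listed in section 16 is not shown, and a key to patient identities is kept through the analysis (sections 11c and 15). All that can be said is that hospital is not listed.

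**Stratification factors are often left to an analysis plan.** That is fair, and section 3d leaves room for further analyses. But the protocol does name the test for the main objective, and the test it names is unstratified. The open clause commits to nothing on hospital or period.

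**Stratifying costs precision in about 150 patients.** True, but the loss is large only where timing and hospital or period strongly overlap, which is where the crude test is least trustworthy.

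**Conclusion.** The point holds in a conditional form. The contradiction over sites is a fact of the document and must be resolved. The stated mortality test takes no account of hospital or calendar period in a non-randomised comparison, and differences between them may therefore be read as a timing effect.

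A reader might go further and conclude that the timing result will be biased, or that the two groups are really two hospitals or two eras. The documents do not support that. Bias requires hospital or period to be related both to PEG timing and to mortality, and the protocol gives no figure for either link.

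Under the assumptions shown, the spurious 3-month difference is 0 to 2 points with little imbalance, 8 to 9 points in the middle range and 18 points with strong imbalance. The false-positive rate of the unstratified log-rank test runs from about 0.05 to about 0.75. Which of these applies can be learned only by tabulating hospital and year against timing group.

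**What to change.** 1. Reconcile sections 2c, 3a, 3b, 3d, 7 (item 5), 15 and the expedited-review justification, so that they name the same contributing hospitals.
2. If more than one hospital contributes, make sure the treating hospital is recorded for each patient, and list it in section 8g.
3. Derive PEG year from the procedure date already listed there, and tabulate timing group by hospital and by year.
4. In section 3d, stratify or adjust the mortality comparison with few strata, for example SLU versus other SSM hospitals and 2011-2012 versus 2013-2014. Use period alone if only SLU contributes. The cut between 2012 and 2013 is a convention and should be fixed before outcomes are examined. Report the crude log-rank test alongside.

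The cost is at most one extra field per chart, a stratified version of a test already planned, and some precision: about 4% of the information with a 60/40 split and 36% with an 80/20 split. If the tabulation shows that nearly all patients in a stratum fall in one timing group, that stratum says little about timing and the report should say so. This adds to adjustment for patient-level prognostic factors and does not replace it.

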5. SSMSL

All research involving SSMSL locations (including Cardinal Glennon), including inpatient or outpatient services and medical record access, requires approval from the SSM STL or SSM Cardinal Glennon Research Business Review (RBR) prior to study initiation. This process is designed to facilitate compliance with state and federal regulations as they pertain to research in hospitals and clinical research billing. While researchers can begin to complete the SSM RBR form at any time, the form should not be submitted until the IRB and the CTO have approved the study. Please contact the SSMSL Office at [name] or [name]. [contact] for more information.

Not Applicable

- X Yes, study requires RBR review
- Does this project require registration on ClinicalTrials.gov, and/or is this project subject to the NIH GCP Training Requirement? (Select "Yes" if either apply)

Registration may be required if any of the following apply: 1) The project meets the FDAAA definition of an "Applicable Clinical Trial", which requires registration on ClinicalTrials.gov. 2) As of January 1, 2017, a new NIH policy mandated biomedical and behavioral "Clinical Trials" to be registered on ClinicalTrials.gov. In addition, NIH policies require personnel on NIH "Clinical Trials" to take GCP training every three years. 3) Registering may be required for Journal Publication (ICMJE). Please review relevant definitions here. Contact the CTO at [contact] with questions about registering on ClinicalTrials.gov and refer to the training page of the IRB website for

Ν

Protocol # 29062 [name]

	CC		

Percutaneous Endoscopic Gastrostomy (PEG) tube placed less than or greater than 7 days post stroke: Mortality, Predictors of Mortality, Complications, and Outcomes.

information on NIH GCP Training requirements.

* * * Subject Population * * *

- 8. Subject Population In the space below, please detail the participants that you are requesting to recruit (include description of each group requested)
- a) Expected age range of subjects. (For example ≥ 18 yrs to 90 yrs).

≥18 years old

b) Number of evaluable subjects to be accrued at SLU or SLU site (this includes all sites under the direction of the SLU PI).

150 patients, 75 patients with PEG placed less than 7 days post stroke and 75 patients with PEG placed greater than or equal to 7 days post stroke

Exceeding the number listed here is a protocol violation. Prior IRB approval is required if additional participants are to be accrued. If applicable, this number should be consistent with your power analysis described in 3d.

c) Number of evaluable subjects to be accrued study wide. *?HELP?*

150 patients,75 patients with PEG placed less than 7 days post stroke and 75 patients with PEG placed greater than or equal to 7 days post stroke

d) If including vulnerable populations (minors, pregnant women and fetuses, neonates, non-English speaking, economically or educationally disadvantaged, prisoners, adults temporarily or permanently unable to consent for themselves): 1) provide the rationale for the importance of including this population in the research, and 2) specify the measures being taken to minimize risks to potentially vulnerable subjects. Click on hyperlinks to access SLU Guidelines containing additional considerations and strategies for mitigating risks.

N/A

Protocol # 29062 [name]

Protocol Title:

Percutaneous Endoscopic Gastrostomy (PEG) tube placed less than or greater than 7 days post stroke: Mortality, Predictors of Mortality, Complications, and Outcomes.

e) If women, minorities, or minors are not included, a clear compelling rationale must be provided unless not applicable. Examples for not including minors: disease does not occur in children; drug or device would interfere with normal growth and development; etc. If federally funded reference appropriate section of the sponsors protocol/grant. *?HELP?*

Minors are not included in the study as acute dysphagic stroke is rarely seen in minors.

- f) If any specifically targeted subjects are students, employees, or laboratory personnel, specify the measures being taken to minimize the risks and the chance of harm to these potentially vulnerable subjects. See SLU Guidelines for additional considerations and strategies for mitigating risks.
- g) Describe how potential subjects will be identified for recruitment (e.g., chart review, referral from individual's treating physician, those individuals answering an ad). How will potential participants learn about the research, and how will they be recruited (e.g., flyer, e-mail, web posting, telephone, etc.)? Upload recruitment materials in the Attachment Section (#16). Important to remember: potential subjects cannot be contacted before IRB approval. NOTE: The use of SLU owned websites in an approved SLU format (e.g., Cancer Center website, etc.) are always approved methods of recruitment.

Data will be collected by means of ICD-9 codes from Epic and diagnosis codes from ProVation. Data will be collected by myself and another member of the research team. The data will be extrapolated and deidentified.

Data will be collected from 2011-2014. Data includes, indication for PEG placement (stroke), date/time procedure was done, date patient was discharged from the hospital, new diagnosis codes post procedure prior to discharge from the hospital, date of death, reason for death, hospital length of stay (date of admission to date of discharge), complications noted in the procedure note or chart documentation by diagnosis code.

Records will be kept on confidential, on a password protected device.

* * * Subject Population * * *

8. Subject Population (continued)

Page numbers from a sponsor's protocol/grant may be referenced in 8h.

h) Inclusion and Exclusion Criteria.

Identify inclusion criteria.

Inclusion criteria: patients who suffered an acute dysphagic stroke, ≥18 years old. Patients who had a PEG tube placed endoscopically through the "pull through" method (not surgically or radiologically placed).

Identify exclusion criteria.

Exclusion criteria include: Other underlying neurologic disorder causing dysphagia NOT stroke, age < 18 years old.

i) Compensation. Explain the amount and schedule of compensation, if any, that will be paid for participation in the study. Include provisions for prorating payment.

Protocol Title:

PROTOCOL Biomedical Research Saint Louis University

Protocol # 29062 **[name]**

days post stroke: Mortal	ity, Predictors of	f Mortálity, C	omplications, a	nd Outcomes

Percutaneous Endoscopic Gastrostomy (PEG) tube placed less than or greater than 7

in the study. Include provisions for prorating payment. N/A

Describe who will cover study related costs. Explain any costs that will be charged to the subject. j) N/A

Estimate the probable duration of the entire study including data analysis and publication. This estimate k) should include the total time each subject is to be involved and the duration the data about the subject is to be collected. If the study is Investigator-initiated, a timeline for individual subject recruitment, follow-up, total time for subject accrual, and data analysis for the study is required.

After IRB approval:

Stage 1: Review medical records, 3-4 months Stage 2: Data collection, 2-3 months

Stage 3: Data analysis, 1 month

Stage 4: Manuscript development for publication, 1 month

* * * Risks * * *

9. Risks

There is no research that can be considered totally risk free (e.g., a potential risk of breach of confidentiality). Therefore, when describing the risk, the lowest level of risk is "no more than minimal risk".

Page numbers from a sponsor's protocol/grant may be referenced in 9.1, 9.2, 9.3, and 9.4.

- Use of investigational devices. Please include the clinical adverse events (AEs) associated with each of the devices with an indication of frequency, severity and reversibility. This information can often be found in the Investigator(s) brochure. NOTE: Include any likely adverse effects associated with procedures that subjects may experience while in the study.
- 2. Use of investigational drugs. Please include the clinical AEs associated with each of the drugs with an indication of frequency, severity and reversibility. This information can often be found in the Investigator(s) brochure. NOTE: Include any likely adverse effects associated with placebos or washout periods that subjects may experience while in the study.
- Use of FDA approved drugs, reagents, chemicals, or biologic products. Please include the clinical AEs associated with each of the drugs with an indication of frequency, severity and reversibility. This information can often be found in the package insert provided by the manufacturer. NOTE: Include any likely adverse effects associated with placebos or washout periods that subjects may experience while in the study.

€-PROTOCOL

a.

Please list the pregnancy category of any drugs or N/A.

PROTOCOL Biomedical Research Saint Louis University

Protocol # 29062 [name]

Protocol Title:	Percutaneous Endoscopic Gastrostomy (PEG) tube placed less than or greater than
	days post stroke, Mortality, Predictors of Mortality, Complications, and Outcomes

days post stroke: Mortality, Predictors of Mortality, Complications, and Outcomes Use of FDA approved devices. Please include the clinical adverse events (AEs) associated with each 4. of the devices with an indication of frequency, severity and reversibility. This information can often be found in the Investigator(s) brochure. NOTE: Include any likely adverse effects associated with procedures that subjects may experience while in the study. 5. Describe any risks related to performing study procedures. Please include all investigational, noninvestigational, and non-invasive procedures (e.g., surgery, blood draws, treadmill tests). Potential risk of loss of confidentiality Describe any risks related to the use of radioisotopes/radiation-producing machines (e.g., X-rays, CT 6. scans, fluoroscopy). 7. Describe why this investigational compound/drug/device/procedure's risks/benefits are potentially better than standard of care or other common alternatives. Any standard treatment that is being withheld must be disclosed and the information must be included in the consent form. *?HELP?* N/A 8. Describe any psychological, social, or legal risks the subject may experience. *?HELP?* Potential risk of loss of confidentiality Page numbers from a sponsor's protocol/grant may be referenced in 9.9 and 9.10. Special Precautions. Describe the planned procedures for protecting against or minimizing potential 9. risks. If appropriate, include the standards for termination of the participation of the individual subject. Discuss plans for ensuring necessary medical or professional intervention in the event of adverse effects to the subjects. N/A 10. Reproductive Risks.

€-PROTOCOL

PROTOCOL Biomedical Research Saint Louis University

Protocol # 29062 [name]

Percutaneous Endoscopic Gastrostomy (PEG) tube placed less than or greater than 7 days post stroke: Mortality, Predictors of Mortality, Complications, and Outcomes.

N/A

b. Please describe any reproductive risk associated with any part of the research study. Include any data from other studies (animal or human).

N/A

b.

Data Safety Monitoring

Federal regulations require that when appropriate, the research protocol makes adequate provisions for monitoring the data to ensure the safety of participants. Monitoring should be commensurate with risks and with the size and complexity of the research, and could range from no plan needed to an independent data safety monitoring board. Please refer to SLU Guidelines for Data and Safety Monitoring as you complete the questions below.

a. Is there a Data Monitoring Committee (DMC) or Board (DSMB)?

If yes, please provide the following information (labeled a-g): a) the composition of the board (degrees/qualifications of members), b) whether the board is independent from the sponsor and research team or not, c) frequency of meetings and issuance of reports to sites, d) assurance that the board is reviewing aggregate safety data and making recommendations regarding study continuance, e) provisions for ad hoc meetings if needed, f) who is reviewing SAEs in real time (MD or DO), and g) stopping/halting rules (if any exist).

A DSM charter can be referenced for all items except for "f) who is reviewing SAEs in real time."

If no, please justify why not.

Is there a Data Safety Monitoring Plan (DSMP)?

N/A

N/A

Note, if all relevant plan information is included in DSMB question above, select 'Yes' and state "see above" in the answer box.

If yes, provide details (labeled a-e) including: a) what types of data or events are captured and how are they documented, b) who is monitoring data, their independence/affiliation with the research and their degrees/qualifications, c) frequency of aggregate data review, d) who is reviewing SAEs in real time (MD or DO), and e) stopping/halting rules (if any exist).

Protocol # 29062 [name]

	ററ		e:

Percutaneous Endoscopic Gastrostomy (PEG) tube placed less than or greater than 7 days post stroke: Mortality, Predictors of Mortality, Complications, and Outcomes.

If no, please justify why not.

- 12. In case of international research (research outside of the U.S. or research on international populations (non-U.S.)), describe qualifications/preparations that enable you to evaluate cultural appropriateness and estimate/minimize risks to subjects. Include whether research is sensitive given cultural norms.
- a. State any local laws/regulations governing Human Subjects Research in the country(ies) you will conduct the research and attach any relevant approvals. If none, state N/A.
- b. Will there be language barriers and if so, how will they be addressed?

Note: If materials are to be distributed to subjects in their native language, please follow SLU's Guidance For Studies Involving Non-English Speaking Subjects.

NOTE: Export control laws include the transfer of technical information and data, as well as information and technology to foreign nationals. If this study has international components, contact the SLU Export Control Officer for direction on whether export control policies apply.

* * * Benefits/Alternatives, Procedures to Maintain Confidentiality and Privacy * * *

10. Benefits/Alternatives

 Benefits. Describe the potential benefit(s) to be gained by the subjects and how the results of the study may benefit future subjects and/or society in general. Indicate if there is no direct benefit to the participants.

There is no direct benefit to the patients studied in this research project. However, results will benefit future post stroke PEG tube patients as we will determine which patients are at lowest risk for morbidity and mortality post PEG placement.

b) Alternatives. Describe any alternative treatments and procedures available to the subjects should they choose not to participate in the study. If no such alternatives exist, please state that the alternative is nonparticipation. For some studies, such as record reviews, a description of alternatives would not be applicable.

N/A

11. Procedures to Maintain Confidentiality and Privacy

Federal regulations require that research materials be kept for a minimum of three (3) years and HIPAA documents be kept for a minimum of six (6) years after the closure of the study. For FDA-regulated or sponsored projects, the PI may be required to keep the data and documents for a longer time period.

Protocol # 29062 [name]

Protocol Title:

Percutaneous Endoscopic Gastrostomy (PEG) tube placed less than or greater than 7 days post stroke: Mortality, Predictors of Mortality, Complications, and Outcomes.

Confidentiality

To determine whether adequate provisions for confidentiality of data are in place, the IRB must ensure that research materials are stored in appropriate locations throughout the study (during collection, transport/transmission, analysis and long term storage). Research information must be protected using appropriate safeguards based on identifiability of the data and risk associated with the study (See SLU IRB Confidentiality Guidelines).

